### **Determination of Dose-Limiting Toxicities**

The patient population used for determination of DLTs will consist of patients who have met the minimum safety evaluation requirements of the study, and/or who have experienced a DLT. Minimum safety requirements will be met if, during Cycle 1 of treatment, the patient receives at least 75% of planned total doses of AC176 and is observed for at least one cycle following the first dose of AC176. The minimum safety requirements must be met for a patient to be included in the MTD-determining population.

Patients who discontinue treatment early due to disease progression or withdrawal will be asked to have all end-of-treatment (EOT) safety evaluations performed as described in the protocol (see Section 7.6). If a patient withdraws from treatment during Cycle 1 due to any reason other than a DLT and does not meet the minimum requirements for inclusion in the MTD-determining population described above, that patient will be replaced.

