**Table 4 Dose-Escalation (3+3) Design**

Number of Patients with a DLT	Action
0 of 3 patients	Escalate to next dose level
1 of 3 patients	Accrue 3 additional evaluable patients at the current dose level (for a total of up to 6 evaluable patients) a
1 of 6 patients	Escalate to the next dose level
2 or more patients in a dose level group of up to 6 patients	The MTD has been exceeded

DLT = dose-limiting toxicity; MTD = maximum-tolerated dose

a For a patient to be considered “evaluable,” he must have met the minimum safety evaluation requirements of the study, and/or experienced a DLT.

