### 5.1.3 Dose-Limiting Toxicity

Toxicity will be assessed using NCI CTCAE Version 5.0 unless otherwise specified.

A toxicity will be considered dose-limiting if it occurs during the first cycle of treatment with AC176 during the dose-escalation phase (excluding Backfill cohort patients). Dose-limiting toxicities (DLTs) will not include any toxicity related to underlying disease (including disease progression), intercurrent illness, concomitant medications, or extraneous causes. DLTs will be defined as follows:

- Any Grade 5 toxicity
- **Hematologic:**
  - Grade 4 neutrophil count decrease for >7 days; or febrile with neutrophil count decrease (ANC <1000/mm^3 with a single temperature of >38.3°C [101°F] or a sustained temperature of ≥ 38°C [100.4°F] for more than 1 hour)
  - Grade 4 platelet count decrease; or Grade 3 platelet count decrease associated with clinically significant bleeding, including any bleeding that warrants a platelet transfusion, related to drug
  - Grade 4 anemia related to drug (life-threatening consequences requiring urgent interventions)
- **Non-Hematologic:**
  - Grade 3 or 4 non-hematologic toxicity, with the **exception of**:
    - Alopecia;
    - Grade 3 nausea, vomiting, or diarrhea if well-controlled by supportive care within 72 hours;
    - Grade 3 skin rash that improves in ≤7 days, with or without supportive care;
    - Grade 3 fatigue that improves in ≤7 days, with or without supportive care;
    - Grade 3 endocrinopathies that only require treatment with hormone replacement therapy;

*CONFIDENTIAL*

Study Drug: AC176

Sponsor/Development Innovations Study Number: AC176-001/GU 207

Final Protocol: 10 July 2023 Version 4.0

- Grade 3 non-hematologic laboratory abnormalities, other than liver function tests, will not be considered a DLT unless they are associated with clinical manifestations which lead to medical intervention and/or hospitalization.
- Potential drug-induced liver injury consistent with Hy's Law (Appendix F), defined as AST and/or ALT  $>3 \times$  ULN with concurrent total bilirubin  $>2 \times$  ULN without findings of cholestasis (alkaline phosphatase [ALP]  $>2 \times$  ULN)
- Grade 3 or higher electrolyte abnormality that lasts  $>72$  hours, unless the patient has clinical symptoms, in which case all Grade 3 or higher electrolyte abnormalities regardless of duration should count as a DLT

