#### **5.1.4 Maximum-Tolerated Dose**

The MTD is the highest dose at which  $\leq 1$  of 6 patients experiences a DLT during Cycle 1 of therapy. If 2 or more patients in a dosing group of  $\leq 6$  patients experience a DLT, the MTD has been exceeded. If 2 or more patients in a dose level group of up to 6 patients experience a DLT and only 3 patients were evaluated at the previous (i.e., next lower) dose, then an additional 3 patients will be evaluated at this next lower dose; and, if 0 or 1 have DLTs, then this previous dose level will be declared the MTD. If 2 or more patients have DLTs, there will be further de-escalation according to the same scheme.

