#### **5.1.5 Intra-Patient Dose Adjustment**

Patients may be permitted an intra-patient dose-escalation of AC176 to a higher dose level that has been cleared and deemed safe by the SRC if they have completed at least 2 cycles at their assigned dose level and continued on study with no  $\geq$  Grade 2 treatment-related AEs. The highest dose the patient can be escalated to is the highest dose level that has been cleared for DLT and is considered to be safe for this patient by the Investigator. The Investigator must consult with the Medical Monitor to confirm that the patient has been tolerating their AC176 dose. The patient data will continue to be collected for evaluation of safety and clinical activity, and all assessments will continue according to the Schedule of Assessments (see applicable SOA Table 2 or Appendix H).

*CONFIDENTIAL*

Study Drug: AC176

Sponsor/Development Innovations Study Number: AC176-001/GU 207

Final Protocol: 10 July 2023 Version 4.0

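### An escalation patient whom AC176 toxicity short of a listed DLT takes below 75% of Cycle 1 doses is left out of the DLT count that defines the MTD

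*Protocol*

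**What the plan says.** Section 5.1.3 (Determination of Dose-Limiting Toxicities) gives two routes into the population used for DLTs and the MTD. Either the patient meets the minimum safety requirements, meaning that during Cycle 1 "the patient receives at least 75% of planned total doses of AC176" and he is observed for at least one cycle, or he has a DLT. Footnote a of Table 4 repeats this for evaluability: "he must have met the minimum safety evaluation requirements of the study, and/or experienced a DLT".

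Replacement does not depend on cause. The rule begins "If a patient withdraws from treatment during Cycle 1 due to any reason other than a DLT" and applies when the minimum requirements are not met. Section 7.6 says the same. A patient who stays on treatment after a long hold is not covered by the replacement sentence, but he is still non-evaluable.

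The DLT list in 5.1.3 has no criterion for missed doses, delay or discontinuation caused by drug-related toxicity. It also leaves some toxicities out on purpose:

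- Platelets: apart from Grade 4, the criterion is "Grade 3 platelet count decrease associated with clinically significant bleeding".
- Neutrophils: apart from the febrile case, it is "Grade 4 neutrophil count decrease for >7 days".
- Laboratory values: "Grade 3 non-hematologic laboratory abnormalities, other than liver function tests, will not be considered a DLT unless they are associated with clinical manifestations" that lead to medical intervention or hospitalization.
- Grade 3 rash or fatigue that improves within 7 days is exempt.

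Section 6 nevertheless holds dosing for these events, and it allows delays of up to 2 weeks for adverse events.

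**The concern.** Being left out for missed doses is harmless when the cause is unrelated to the drug. Here the cause can be the drug itself, so the exclusion is informative: a patient who could not take the dose because of AC176 is removed from the count meant to show whether the dose can be taken.

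That count has consequences. Section 5.1.4 defines the MTD by it ("The MTD is the highest dose at which" at most 1 of 6 patients has a Cycle 1 DLT). Section 5.1.6 makes the MTD the ceiling for the RP2D. Section 5.1.5 uses it as one condition for raising a patient's own dose: "The highest dose the patient can be escalated to is the highest dose level that has been cleared for DLT". With 3 to 6 patients per level, one patient's classification can change the action in Table 4.

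**Working it through.** The protocol gives no figure on this point to reproduce. The check has three parts: whether the rules produce the case, how many missed doses it takes, and what one such patient does to Table 4.

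**1. Do the protocol's own hold rules produce the case?**

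- *Grade 3 platelets without significant bleeding.* Not a DLT. Table 5 holds dosing until platelets reach 75 × 10⁹/L and provides for resolution in more than 7 days but under 2 weeks, that is 8 to 13 days. Section 5.3.1 bars growth factors and transfusions during the Cycle 1 DLT period, so recovery cannot be hastened that way.
- *Afebrile Grade 4 neutrophils for 7 days or less.* Not a DLT. Table 5 holds until ANC is at least 1.0 × 10⁹/L. For example, 6 days at Grade 4 plus 4 days at Grade 3 is a 10-day hold.
- *Asymptomatic Grade 3 creatine kinase rise.* Not a DLT. Table 6 holds until Grade 1 or baseline and again provides for more than 7 days and under 2 weeks.
- *Grade 3 rash or fatigue improving within 7 days.* Not a DLT. Table 6 holds until Grade 1, baseline or tolerable Grade 2. This matters mainly on the 14-dose schedules below.

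**2. How many missed doses make a patient non-evaluable?** The threshold is 0.75 × planned Cycle 1 doses, rounded up.

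| Schedule | Planned doses | Needed | Missed doses that fail | Share then received |
|---|---|---|---|---|
| Once daily, 28 days | 28 | 21 | 8 | 20/28 = 71% |
| 3 weeks on / 1 off | 21 | 16 | 6 | 15/21 = 71% |
| 5 days on / 2 off | 20 | 15 | 6 | 14/20 = 70% |
| 4 days on / 3 off | 16 | 12 | 5 | 11/16 = 69% |
| 2 weeks on / 1 or 2 off; 7 days on / 7 off | 14 | 11 | 4 | 10/14 = 71% |

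On once-daily dosing a 7-day hold gives 21/28 = 75.0% and still qualifies. An 8-day hold gives 71.4%, a 10-day hold 18/28 = 64.3% and a 13-day hold 15/28 = 53.6%. The 8-day hold must start by Day 21. On a 14-dose cycle, a 4- to 7-day hold falling on dosing days leaves 10/14 to 7/14, or 71% to 50%.

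**3. What does one such patient do to Table 4?** Three evaluable patients without a DLT plus one such patient read as 0 of 3, which is an escalation. If his event were ruled dose-limiting, the level would have one DLT and go to 6 evaluable patients.

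**Illustration with assumed rates.** The chance that a level clears on the count is P = (1−p)³ + 3p(1−p)⁵, where p is the DLT probability per evaluable patient. Assume a listed-DLT rate d = 0.10 and a rate u of toxicity-driven under-dosing without a listed DLT. Neither rate is in the protocol, and no SRC action is modelled.

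| u | As written, p = d/(1−u) | All ruled dose-limiting, p = d+u |
|---|---|---|
| 0.02 | p = 0.102, P = 0.903 | p = 0.12, P = 0.871 |
| 0.05 | p = 0.105, P = 0.897 | p = 0.15, P = 0.814 |
| 0.10 | p = 0.111, P = 0.887 | p = 0.20, P = 0.709 |

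If the SRC ruled none of these events dose-limiting and replaced the patients, the middle column would stand. Keeping them as evaluable and DLT-free (p = 0.10) would give 0.906, slightly more permissive than the present rule, so that is not a remedy.

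**The case against.** The strongest reply is that the count is not the only control. Section 10.5.3 has the SRC review all available safety data, take interruptions and reductions into account, and document its decision-making before new patients are dosed. It can expand, de-escalate or stop. Section 5.1.1 bases escalation on the safety profile and PK as well as DLTs. Section 5.1.5 also requires that the SRC has deemed the level safe, that the Investigator agrees, that the Medical Monitor is consulted and that the patient has had no treatment-related AE of Grade 2 or higher. The MTD is only a ceiling on the RP2D. All of this stands. A reader might infer from the exclusion that the toxicity goes unseen or that escalation proceeds without a record; the documents do not support that.

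The DLT thresholds also look deliberate, and preferring others would be a matter of taste. That stands too. The point is not that non-bleeding Grade 3 thrombocytopenia should always be a DLT. It is that when such an event costs a patient more than a quarter of his doses, he drops out of the count altogether.

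On once-daily dosing the route is narrow. Most Grade 3 or 4 non-hematologic toxicities are already DLTs, toxicity of Grade 2 or lower normally continues without a dose reduction, and the scheduled Cycle 1 laboratory checks after Day 1 fall on Days 8 and 15. The present rule also never credits an under-dosed patient with having tolerated the dose.

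What the reply does not supply is a rule by which the SRC can put this patient into the Table 4 or MTD count. Its one include-or-exclude power in 10.5.3 concerns patients treated despite failing eligibility who are otherwise evaluable.

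**Conclusion.** The concern holds in a limited form. Followed exactly, 5.1.3 and Table 4 footnote a remove from the MTD-defining count an escalation patient whom AC176-related toxicity short of a listed DLT takes below 75% of planned Cycle 1 doses. It takes 8 or more missed doses on a 28-dose once-daily cycle, and 4 on a 14-dose intermittent cycle if the SRC opens one.

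A reader might go further and infer that the MTD will be set too high. The protocol does not support that. It gives no rate for such holds, the count understates toxicity only so far as the events ought to be dose-limiting, and the SRC can act on them without the count. The probabilities above (0.90 to 0.89 as written, against 0.87 to 0.71 if every such event were ruled a DLT) rest wholly on the assumed rates of 10% and 2% to 10%, and there is no change if none is so ruled. The defect is a gap in a counting rule, not a failure of safety oversight.

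**What to change.** Add to Sections 5.1.3 and 7.6: for any escalation patient who falls below 75% of planned Cycle 1 doses because of AC176-related toxicity without a listed DLT, the SRC must decide before clearing the level whether the event is dose-limiting, and must give the decision in the record that Section 10.5.3 already requires. If it is dose-limiting, the patient counts as a DLT in Table 4 and for the MTD. If it is not, he may be replaced and is reported beside the DLT count.

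This is a new SRC power alongside the fixed DLT list and should be described as such. It is not an extension of the rule for patients treated in error, which decides only on inclusion and does not reclassify events.

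The cost is a few sentences and a line in the SRC record. The downside is some case-by-case judgment beside a fixed list, and occasionally a second group of 3 patients before a level is cleared.

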## **7.6 Early Patient Termination/Patient Withdrawal**

Patients who discontinue treatment early due to disease progression, unacceptable toxicity, intolerance, or withdrawal of consent will be asked to have all EOT safety evaluations performed as described in the protocol (see the applicable SOA table). If a patient withdraws from treatment during Cycle 1 due to any reason other than a DLT and does not meet the minimum requirements for inclusion in the MTD-determining population described in Section 5.1.4, that patient will be replaced.

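### Section 5.1.3 contradicts itself on whether a patient with an early Cycle 1 DLT counts toward the MTD

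*Protocol*

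**What the plan says.** The subsection Determination of Dose-Limiting Toxicities in Section 5.1.3 opens by defining the population for determining DLTs as "patients who have met the minimum safety evaluation requirements of the study, and/or who have experienced a DLT". It then defines the minimum safety requirements: during Cycle 1, "the patient receives at least 75% of planned total doses of AC176 and is observed for at least one cycle" after the first dose. The next sentence reads: "The minimum safety requirements must be met for a patient to be included in the MTD-determining population". This sentence is in the current Version 4.0 text, and Appendix I lists it as an addition made in that version.

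Four provisions keep a patient with a DLT in the count:

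- The opening sentence of the subsection, just quoted.
- Table 4, footnote a: to be evaluable, "he must have met the minimum safety evaluation requirements of the study, and/or experienced a DLT".
- Section 5.1.4: if 2 or more "patients experience a DLT, the MTD has been exceeded". No dose-intake or observation condition is attached.
- The replacement rule, in Section 5.1.3 and again in Section 7.6. It begins "If a patient withdraws from treatment during Cycle 1 due to any reason other than a DLT", so a patient who leaves because of a DLT is not replaced and, by implication, keeps his place.

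Section 7.6 refers to the "MTD-determining population described in Section 5.1.4, that patient will be replaced". Section 5.1.4 does not mention that population, and Section 10.3 (Analysis Population) does not define it.

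**The concern.** The 3+3 count sets the MTD, and Section 5.1.6 caps the RP2D at the MTD. If the sentence with no DLT alternative is applied as written, a patient whose DLT came early, or was fatal, can fall outside the population that determines the MTD. The patients in dispute are thus those with the earliest or most severe toxicity. They would be neither counted nor replaced, while Section 5.1.1 still requires at least 3 patients who completed a cycle and are evaluable before the next level opens. Two careful readers could take different numerators and denominators from the same cohort, in a first-in-human study where escalation is decided on groups of 3 to 6.

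**Working it through.** The protocol states no operating characteristics for its 3+3 rule, so there is no figure to reproduce. The check has two parts: whether the conflict can occur under the protocol's own rules, and what it could do to the count.

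**1. Can a DLT patient fail the minimum requirements?**

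Inputs: 28-day cycle (Table 2 footnotes), continuous once-daily dosing (Section 5.1), 75% threshold (Section 5.1.3). Planned doses are 28, and the threshold is 0.75 × 28 = 21.

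- *Grade 5 toxicity in Cycle 1.* The patient is not observed for a full cycle, so he fails whatever his dose intake.
- *"Grade 4 neutrophil count decrease for >7 days"* (a DLT in Section 5.1.3). Table 5 holds the dose for Grade 4 neutrophil decrease. If 8 or more daily doses are held within Cycle 1, at most 28 − 8 = 20 are taken, and 20/28 = 71.4%, which fails. For twice-daily dosing, (56 − 16)/56 = 40/56 = 71.4%, which also fails.
- *Grade 4 non-hematologic DLT that Table 6 makes a discontinuation.* The patient fails if fewer than 21 daily doses were taken.

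The intermittent schedules plan 14 to 21 dosing days per cycle, so the numbers shift, but the sentence still has no DLT alternative.

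**2. What could it do to the count?**

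Let p be the true Cycle 1 DLT rate and f the share of DLT patients who miss the minimum requirements. The protocol gives neither, so both are assumptions: p = 50% and 33%, f = 25% and 50%.

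(a) Every DLT patient counts: P(clear) = (1−p)³ + 3p(1−p)⁵.
- p = 0.50: 0.125 + 0.047 = 0.172
- p = 0.33: 0.301 + 0.134 = 0.434

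(b) Literal sentence, uncounted patients refilled: the DLT rate among counted patients is q = p(1−f)/(1−pf), and P(clear) = (1−q)³ + 3q(1−q)⁵.
- p = 0.50, f = 0.50: q = 0.25/0.75 = 0.333, result 0.428
- p = 0.33, f = 0.50: q = 0.165/0.835 = 0.198, result 0.714
- p = 0.50, f = 0.25: q = 0.375/0.875 = 0.429, result 0.265
- p = 0.33, f = 0.25: q = 0.2475/0.9175 = 0.270, result 0.558

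(c) Literal sentence, no refilling: a level clears only if no patient is uncounted, so P(clear) = (1−p)³ + 3p(1−f)(1−p)⁵.
- p = 0.50, f = 0.50: 0.125 + 0.023 = 0.148
- p = 0.33, f = 0.50: 0.301 + 0.067 = 0.368

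(d) Chance that a first cohort of 3 includes at least one uncounted DLT patient: 1 − (1−pf)³.
- p = 0.50, f = 0.50: 1 − 0.75³ = 0.578
- p = 0.33, f = 0.50: 1 − 0.835³ = 0.418

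| p | f | (a) all counted | (b) literal, refilled | (c) literal, not refilled | (d) first cohort short |
|---|---|---|---|---|---|
| 50% | 50% | 17% | 43% | 15% | 58% |
| 33% | 50% | 43% | 71% | 37% | 42% |
| 50% | 25% | 17% | 26% | – | – |
| 33% | 25% | 43% | 56% | – | – |

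**The case against.** The strongest reply is that the disputed sentence does not run the escalation. Table 4 works on patients with a DLT and on evaluable patients, and its footnote makes a DLT patient evaluable. Section 5.1.4 counts DLTs directly. Neither uses the term MTD-determining population, which otherwise appears only in a replacement rule that already sets DLT withdrawals aside. On that view the sentence is meant only to say when a patient without a DLT must be replaced, and a site or SRC following Table 4 would count the DLT patient. In addition, Section 10.5.3 puts all available safety data before the SRC, so a Cycle 1 death would be seen whatever the population is called.

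Much of this stands. The weight of the text does favour counting these patients. The larger clearance probabilities need refilling, and the replacement rule does not provide for it. Without refilling, clearance becomes slightly less likely (15% against 17%, and 37% against 43%), and the more likely effect is a stalled cohort. The figures for short cohorts apply only if the MTD-determining population is the one that supplies the 3 required patients.

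Three things do not fall away. The sentence is mandatory in form and nothing limits it to patients without a DLT. Table 4's footnote does not fully settle the short-cohort point, because Section 5.1.1 asks for patients who completed a cycle of treatment as well as being evaluable. Reading the DLT and MTD populations as deliberately different does not work either: Section 5.1.4 derives the MTD from DLT counts alone.

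**Conclusion.** The contradiction is real and lies in the current text. One sentence in Section 5.1.3 excludes from the MTD count any patient below 75% of doses or a full cycle of observation, DLT or not, and four other provisions keep DLT patients in. The protocol's own DLT definitions and dose-modification tables produce patients who fall between the two. No assumption is needed for that conclusion.

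The size of the effect cannot be fixed from the protocol. The probabilities above are illustrations that depend on assumed values of p and f and on whether excluded patients are refilled. Wrongful clearance of a dose level is a possibility under the literal sentence, not a demonstrated outcome. The point should be fixed because the rule determines the MTD and hence the upper limit for the RP2D.

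**What to change.** Reconcile the sentence with the opening sentence of the subsection, Table 4 footnote a, Section 5.1.4 and the replacement rule by adding to it the DLT alternative that the protocol already uses in two of those places. State that the DLT-evaluable and MTD-determining populations are the same. In Section 7.6, change the cross-reference for this population from Section 5.1.4 to Section 5.1.3. Check any cohort already cleared under Version 4.0 against the reconciled wording.

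The cost is one clause, one statement and one cross-reference in a protocol amendment. It needs no extra patients or procedures and changes no dose.

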#### **5.1.4 Maximum-Tolerated Dose**

The MTD is the highest dose at which  $\leq 1$  of 6 patients experiences a DLT during Cycle 1 of therapy. If 2 or more patients in a dosing group of  $\leq 6$  patients experience a DLT, the MTD has been exceeded. If 2 or more patients in a dose level group of up to 6 patients experience a DLT and only 3 patients were evaluated at the previous (i.e., next lower) dose, then an additional 3 patients will be evaluated at this next lower dose; and, if 0 or 1 have DLTs, then this previous dose level will be declared the MTD. If 2 or more patients have DLTs, there will be further de-escalation according to the same scheme.

